Aims 8/9: We will offer enrollment to the 80 participants already enrolled in the InTSHA study. Participants will attend one additional research visit at least 12 months after completion of the intervention in the intervention group and 12 months after randomization for the control group. During the visit, participants will complete a follow-up questionnaire and have a blood draw. All participants will have a viral load assessment.

V. Procedures for obtaining informed consent (including timing of consent process)

Aims 1-2 and 4-7: Since adolescents in South Africa do not require parental/caregiver consent for clinical care, many of them attend clinical appointments without an adult caregiver present. We will offer enrollment to unaccompanied minors ages 15 to 18 if they are interested. With their assent, we will contact their caregiver via telephone to obtain telephone consent with the assistance of the attached telephone consent script. If the adolescent is accompanied by an adult caregiver, a trained research assistant fluent in English and Zulu will obtain written consent from guardians in Zulu or English for adolescents aged less than 18 years old and assent from the adolescent participants. Written assent will be obtained from all participants under the age of 18 years. Informed consent from caregivers will be obtained for the prospective implementation of all proposed study protocols for adolescents less than 18 years old that have given assent to participation either in person or via telephone. Adolescents under the age of 18 years who do not assent to participate in the research will not be able to participate. Adolescents 18 years old or older will provide their own consent.

Aim 3,8,9: Since this is an intervention study, we will require written assent from all participants under the age of 18 years. Informed consent from caregivers will be obtained for the prospective implementation of all proposed study protocols for adolescents less than 18 years old that have given assent to participation either in person or via telephone. Adolescents under the age of 18 years who do not assent to participate in the research will not be able to participate. Adolescents 18 years old or older will provide their own consent. For aims 8 and 9 participants will be asked to re-consent to be in the extended study.

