Aim 6: The same subjects enrolled in Aim 3 will be provided with a pre- and post- intervention questionnaire. During visit one, we will collect data on an additional 9 questions about consent, contraception, family planning, social pressures, and communication related to SRH. The second research visit will take place 6 months after randomization, after the intervention has been completed, to assess changes in beliefs and attitudes towards SRH over time.

Data to be collected and when the data is to be collected

InTSHA: Interactive Transition Support for HIV-infected Adolescents Using Social Media - Detailed Protocol

An additional 9 questions about attitudes and beliefs on SRH will be collected by adding to the existing pre and post questionnaire.

Aim 7: We will recruit participants from adolescents who participated in the clinical trial in Aim 3 from Mahatma Gandhi Hospital's and KwaMashu Poly Clinic's Pediatric and Adult HIV Clinics. Adolescent participants will be identified and referred by the hospital clinicians after clinic visits. We will conveniently sample up to 20 adolescents (based on saturation of major themes) who completed the intervention. We will attempt to enroll equal number of male and female participants of varying ages. Interviews will be conducted in isiZulu or English and last about 1 hour. **Measures:** The in-depth interviews will evaluate personal experiences with sexual and reproductive health as adolescents living with HIV based on the Theory of Planned Behavior and how our mobile health intervention affected attitudes and beliefs of sexual and reproductive health. We will aim for thematic saturation in each group.

Aims 8: We will recruit only patient previously enrolled in the InTSHA study. Participants will complete the same follow-up questionnaire that was completed at the end of the study. Participants will have a single blood draw to evaluate long term viral suppression.

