Aim 8: We will measure of retention in care (pharmacy refill and clinic attendance in last 6 months) and viral suppression (<200 copies/ml) comparing results from 6 months after randomization to 12 months after randomization. In addition, we will explore other factors based on modifiable variables in the SMART model including: adolescent peer support (Child and Adolescent Social Support Scale), (41) self-esteem (Rosenberg scale), (42) depression (PHQ-9), (43) and stigma (Internalized AIDS stigma scale), (44) connection to clinic (Working Alliance Inventory), (45) and transition readiness (HIV Adolescent Readiness for Transition). (46)

Aim 9: We will compare short term adherence (tenofovir levels) among adolescents in the InTSHA intervention group to the standard of care group. In addition, for viremic adolescents we will evaluate for the presence of HIV drug resistance searching specifically for Protease, Integrase, and Reverse Transcriptase mutations. We will use the Stanford database of HIV Drug resistance to determine significant HIV drug resistance mutations.

Modifiable factors from SMART model

- HIV knowledge
- Self-efficacy
- Beliefs
- Maturity
- Goals/Motivation
- Peer and social support
- Relationship with clinical staff
- Experience with HIV disclosure and stigma

Statistical methods

InTSHA: Interactive Transition Support for HIV-infected Adolescents Using Social Media - Detailed Protocol

Aim 1: We will use an inductive, content analytic approach to identify benefits and potential negative impacts of social media use during transition to adult care.(32, 51) Interviews will be translated from the local language (Zulu) into English and transcribed. Transcriptions will be uploaded, organized, and coded using Dedoose software (version 7.0.23, LA, California).(52) We will use open coding to inductively construct descriptive categories based on themes identified in the interviews. We will create a codebook based on themes identified in a subset of interviews. We will use an iterative process to construct categories based on the coded text. Broader themes will be created using linking and framing of coded text.

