Aim 8: We will summarize viral suppression and retention in care in the intervention and control groups using standard summary statistics (e.g. counts/percentages; median and interquartile range of continuous measures). We will estimate the difference between the intervention group and the control for social support, connection to clinic, self-esteem, retention in care and virological suppression 12 months after randomization. The standard deviation for these differences is expected to be on the order of 8%. Depending on the number of individuals not retained in care or the number not virologically suppressed, we may use logistic regression to explore combinations of 2-3 variables potentially predictive of outcome.

Aim 9: We will summarize adherence (tenofovir levels) and significant HIV drug resistance in the intervention and control groups using standard summary statistics (e.g. counts/percentages; median and interquartile range of continuous measures). Although this study is not powered to detect a significant difference in the intervention and control arms for adherence or drug resistance, this will provide valuable explanatory detail for the primary results of this study.

VIII. Risks and Discomforts

Risk: Loss of privacy is a potential risk if information is compromised which could lead to unintended disclosure of personal medical information including HIV status.

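### Aim 8 compares the arms 12 months after randomization, but its visit falls later than that in the intervention arm only

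*Combined protocol and SAP*

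**What the plan says.** Section II describes Aim 8 as an evaluation of impact 12 months after randomization. Later sections fix the details:

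- **Time of the comparison.** Section VII, Statistical methods, Aim 8 plans an estimated difference between arms for several scales and for "retention in care and virological suppression 12 months after randomization". Section VII, Outcomes, Aim 8 also plans "viral suppression (<200 copies/ml) comparing results from 6 months after randomization to 12 months after randomization".
- **Retention.** The same Outcomes paragraph reads "We will measure of retention in care (pharmacy refill and clinic attendance in last 6 months". It does not say from which date the six months are counted back.
- **Time of the visit.** Section IV, Aims 8/9 offers entry to all 80 participants and places the one additional visit "at least 12 months after completion of the intervention in the intervention group and 12 months after randomization for the control group".
- **Suppression.** Section VI, Aim 8: "Participants will have a single blood draw to evaluate long term viral suppression". The same draw serves the tenofovir levels and genotyping of Aim 9.
- **End of the intervention.** Section VI, Aim 6, which concerns the Aim 3 participants: "The second research visit will take place 6 months after randomization, after the intervention has been completed". The length of the intervention is not given.
- **Entry.** Section V: "For aims 8 and 9 participants will be asked to re-consent to be in the extended study".

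No section states an analysis set for Aim 8, or how to count a randomized participant who does not re-enrol or has no result.

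**The concern.** The visit and the comparison it feeds are timed from different origins. The statistical methods place both arms at one time since randomization. The visit schedule counts from randomization in the control arm and from completion of the intervention in the other. Completion comes some time after randomization, so a team that follows section IV cannot deliver what section VII describes.

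Retention and suppression can both change with time in this population; the plan's own premise is that outcomes worsen around transition. If one arm is observed later, part of any difference reflects elapsed time and not the intervention. Randomization does not protect against this, because the timing rule itself depends on the arm. Full attendance does not remove it either.

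A smaller matter sits beside it. Entry depends on re-consent and attendance, attendance is plausibly related to retention, and the plan does not say how participants with unknown status are reported.

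**Working it through.** **1. The plan's own figure.** The documents give no figure for a timing effect. The only number attached to Aim 8 is the expected standard deviation of about 8% for the differences. Read as the standard error of a difference in proportions, √(2p(1−p)/n), it reproduces with n = 40 per arm and an assumed p = 0.85: √(2 × 0.85 × 0.15 / 40) = 0.080. It also reproduces with n = 28 and p = 0.90: √(2 × 0.90 × 0.10 / 28) = 0.080. So it identifies neither an analysis set nor a visit time.

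**2. Visit month.** Let c be the months from randomization to completion. Section VI, Aim 6 implies 0 < c ≤ 6. From section IV, the control visit is at month 12 and the earliest intervention visit is at month 12 + c. The value c = 6 is the latest that Aim 6 allows; c = 3 is an assumption to show the range.

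| | Control | Intervention, c = 3 | Intervention, c = 6 |
|---|---|---|---|
| Earliest visit (month) | 12 | 15 | 18 |
| Six-month look-back, if counted from the visit | 6 to 12 | 9 to 15 | 12 to 18 |
| Overlap with the control look-back (6 − c months) | – | 3 | 0 |
| Time since the month-6 visit (months) | 6 | 9 | 12 |

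The last row shows that the planned comparison of month 6 with month 12 also spans different intervals in the two arms. The intervention arm has a minimum and no upper limit. If the minimum is read as applying to controls too, the earliest visits still differ by c and neither arm has an upper limit.

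**3. What depends on the reading.** If the retention look-back is counted from the visit, the windows differ by arm and a participant with no visit has no window. If it is counted from month 12, the retention windows agree. Suppression is planned from the visit draw, so it is taken later in the intervention arm under either reading.

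**4. Illustration of size.** Assume a constant monthly loss h from care, equal in both arms, with no return and no true effect. The share still in care at month t is (1 − h)^t.

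- h = 1%: 0.99^12 = 88.6%, 0.99^15 = 86.0%, 0.99^18 = 83.5%. Gaps from month 12, before rounding: 2.6 and 5.2 points.
- h = 2%: 0.98^12 = 78.5%, 0.98^15 = 73.9%, 0.98^18 = 69.5%. Gaps: 4.6 and 9.0 points.

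Under these assumptions the whole gap is spurious and counts against the intervention. The documents give no loss rate, so both rates are assumed.

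**5. Unknown participants.** With 40 per arm, each moves that arm's rate by up to 1/40 = 2.5 points. Suppose 36 of 40 and 32 of 40 attend, with 31 and 27 suppressed (assumed counts). The extremes for the arm difference are 31/40 − 35/40 = −10 points and 35/40 − 27/40 = +20 points.

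**The case against.** **Records could supply a common time.** Section VI provides for refill and appointment data, electronic records and a tracker, and section VIII provides for tracing. This stands for retention if the window is fixed from randomization, which the plan does not do. It helps less with suppression: chart review lists the last viral load, but Aim 8 plans suppression from the visit draw. The record review described for Aim 3 covers the period before and 6 months after enrolment.

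**Twelve months after completion may be deliberate**, to measure durability. That is a sensible question within the intervention arm. It does not support a contrast with controls seen at a different time since randomization, or the label used in section VII.

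**The illustration is not the plan's outcome.** It gives status on the visit date, not contact in the last six months. This is correct. If any contact in the look-back counts, the figures for c = 6 become 0.99^6 = 94.1% against 0.99^12 = 88.6% (5.5 points) and 0.98^6 = 88.6% against 0.98^12 = 78.5% (10.1 points). The levels change and the gaps stay similar. The assumption of no return also sits poorly with planned tracing.

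**Stronger readings that the documents do not support:**

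- A reader might infer that only re-enrollers will be analysed. The plan does not say so; it offers entry to all 80 and compares the groups, which leaves an as-randomized reading open.
- A reader might see a clash between the Aim 3 suppression cut-off of <400 copies/ml and the Aim 8 cut-off of <200. On its plain wording the Aim 8 sentence applies <200 to both of its time points, and Aim 3 defines a different outcome.
- A reader might treat the 8% as a tolerance that missing participants could exceed. It is given as a standard deviation.

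**Conclusion.** The point holds at low severity. Section IV contradicts the Aim 8 time point in sections II and VII. Followed as written, suppression is measured later after randomization in the intervention arm, and so is retention if its look-back runs from the visit. The displacement equals the time to complete the intervention: more than zero, and 6 months if completion is at month 6, with no upper limit on the visit. This follows from the text alone, given that the intervention takes time.

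The effect on the arm difference cannot be estimated from the documents. The 5.2 to 9.0 points (2.6 to 4.6 if the intervention ends at month 3) are an illustration that rests on the assumed loss rates, no return and no true effect. The direction also depends on how outcomes move with time.

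The absence of an analysis set is missing detail and a secondary reporting matter, not evidence of a biased analysis. Aim 8 has no test, power statement or decision rule. The Aim 3 primary outcomes and the decision on a larger trial, which uses 6-month data, are not affected.

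**What to change.** 1. Reconcile section IV, Aims 8/9 with Aim 8 in sections II and VII, so that the visit has the same origin and the same window, with an upper limit, in both arms, counted from randomization.
2. Define the six-month retention look-back in months from randomization, so that it also applies to participants with no visit.
3. If visits have already taken place on different schedules, report time since randomization by arm, take retention from records over a common window where consent allows, and label the suppression comparison as made at different times.
4. As a secondary point, analyse by assigned arm, report re-consent and attendance out of 40 per arm, and give the arm difference with participants of unknown status counted both ways. A single rule that counts missing as not suppressed is not recommended as the main analysis. With true suppression of 75% in both arms and 28/40 against 36/40 attending (all assumed), it gives 0.75 × 28/40 = 52.5% against 0.75 × 36/40 = 67.5%, a spurious 15 points.

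**Cost.** Amendment wording, plus record look-up for at most 80 participants in systems already in use. The list linking study numbers to medical records, which section VIII says will be deleted once data are collected, must be kept until then. The ethics committees must confirm whether the Aim 3 consent to record review covers month 12; the consent forms are not in the file. If it does not, only bounds are available for those who do not re-enrol, and they may be wide. Aligning on month 12 gives up a full 12 months of observation after completion; keeping that would need a later visit at the same month in both arms.

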AIM 3: After the development of the behavioral intervention delivered through social media in Aim 2, we will offer enrollment to all adolescents living with HIV at Mahatma Gandhi Hospital and KwaMashu Poly Clinic after their physician determines that they are ready to transfer to adult care. Informed consent and assent will be obtained as in the above procedure. The consent/assent procedure will obtain consent for medical records review.

Adolescents will be randomized (1:1) to receive the behavioral intervention delivered via social media vs. standard of care. All participants will be shown how to password protect their mobile phones. Participants will complete a questionnaire at baseline and after six months to evaluate peer support, connection to clinic, depression, self-esteem and transition readiness. We will conduct in-depth interviews with adolescents in the intervention arm to assess acceptability. We will perform a medical records review and evaluate clinic attendance and viral load before and 6 months after the enrollment.

AIM 4: We will offer enrollment to adolescents living with HIV (ages 15-19 years old) accessing antiretroviral therapy at Mahatma Gandhi Hospital and KwaMashu Poly Clinic, those that have transitioned to adult care, and those who were lost to care as determined by a prior research study. Participants will be referred to study staff by HIV clinicians. We will also offer enrollment to adolescents who participated in in depth interviews for AIM 1 of this study. Participants will complete in-depth interviews exploring the different mechanisms of stigma using the HIV Stigma Framework, including enacted, anticipated, and internalized stigma, and its impact on their engagement in HIV care during healthcare transition.

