Aim 2: The initial version of the InTSHA social media intervention will be based on data in Aim 1 and existing adolescent-friendly curriculum.(33, 34) We will then theatre test the intervention by demonstrating the InTSHA intervention with participants and allowing them to interact on the social media platform. We will also demonstrate the use of educational content delivery, facilitated group discussions, message boards, and meet-ups via social media. We will then use an iterative process with 2 separate focus groups of 8 - 10 adolescents each, 2 focus groups of 8–10 healthcare providers each, and one focus group of 8 - 10 caregivers who have used the InTSHA intervention. Focus groups will be conducted separately for English and Zulu and will last approximately 90 minutes. Analysis: We will analyze the intervention development using the plan, engage, execute, reflect and evaluate process.(35, 36) We will then conduct the focus group based on the UTAUT model of technology acceptance to reflect on usefulness and acceptability the intervention.(37) The focus group discussions will evaluate the usability, challenges, and expectations of the intervention. The discussions will be recorded, transcribed, and translated into English. Transcriptions will be uploaded, organized, and coded using Dedoose software (version 7.0.23, LA, California).(38) We will then use an iterative process after each round of focus group session (adolescents, healthcare providers, and caregivers) to evaluate feedback for each version of the intervention based on coded themes identified during focus group feedback sessions. The intervention will subsequently be revised based on focus group feedback prior to demonstration with the next round of focus group participants. The final intervention will be based on the iterative process from all focus groups as well as input from our collaborative research team. To ensure fidelity of the intervention, we will use an intervention manual for content with training of the research team and healthcare providers. Only one team will monitor and facilitate the sessions.

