Aim 3: Recruitment will take place over 15 months. We anticipate enrolling groups of 5 - 10 subjects based on preferences defined in Aim 1. During visit one, we will collect baseline demographic data, baseline questionnaires, and have viral load assessments on all participants. The second research visit will take place 6 months after randomization. This research visit will evaluate acceptability and feasibility and perform in-depth interviews exploring the UTAUT model of technology acceptance with all participants in the experimental arm.(37) In addition, all subjects will complete follow-up questionnaires and have viral load assessment.

Data to be collected and when the data is to be collected

Demographic data will be collected on all adolescents during a chart review and will include age, sex, age at diagnosis, history of opportunistic infections, length of time on ART, ART regimen, last viral load, last clinic visit, and last pharmacy refill. Data will be collected from a combination of electronic records (Tier.net and NHLS) and paper charts. Additional data on vital status and location of care services will be obtained through the tracker program. Only de-identified data will be entered into the database. Viral load will be measured at enrollment and 6 months after randomization. Pharmacy refill and clinic appointment data will be collected during enrollment in the study.

InTSHA: Interactive Transition Support for HIV-infected Adolescents Using Social Media - Detailed Protocol

Aim 4: We will recruit participants from adolescents who participated in AIM 1 interviews, and from Mahatma Gandhi Hospital's and KwaMashu Poly Clinic's Pediatric and Adult HIV Clinics.

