Aim 3: Our primary focus is on estimating the acceptability and feasibility of the social media intervention for planning a larger clinical trial to measure efficacy. We will consider a feasibility / acceptability estimate of 80% or higher among the 40 participants as evidence that the social media program is acceptable to the population. Analysis. We will summarize the acceptability and feasibility data in the intervention group using standard summary statistics (e.g. counts/percentages; median and interquartile range of continuous measures). We will estimate the difference between the intervention group and the control for social support, connection to clinic, self-esteem, retention in care and virological suppression 6 months after randomization. The secondary outcomes will assist in planning a larger randomized clinical trial through a future R01 grant; the standard deviation for these differences is expected to be on the order of 8%. Depending on the number of individuals not retained in care or the number not virologically suppressed, we may use logistic regression to explore combinations of 2-3 variables potentially predictive of outcome. Assuming that the intervention is acceptable and feasible for participants, we would consider moving forward to an R01 if there was evidence of a benefit to participants, in terms of overall retention and virological suppression at 6 months, although we would not expect the difference to be statistically significant.

Power analysis (sample size, evaluable subjects, etc): With 40 participants in the experimental arm, if the true acceptability rate were 90% we would be able to rule out that acceptability was less than 70% with 90% power (alpha=0.05, one-sided) using an exact test.

Aim 4: We will use an inductive, content analytic approach to identify the different mechanisms of stigma and how they affect engagement in care during healthcare transition. Interviews will be recorded, transcribed, and translated into English. Transcriptions will be uploaded, organized, and coded using Dedoose software (version 7.0.23, LA, California).(52) We will use open coding to inductively construct descriptive categories based on themes identified in the interviews and then create a codebook based on themes identified in a subset of interviews. We will create categories based on the coded text using an iterative process and broader themes will be created using linking and framing of coded text.

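### Does sharing an online group in the intervention arm only mean the pilot's power statement and between-arm analyses must allow for clustering?

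*Combined protocol and SAP*

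**What the plan says.** Section IV (Aim 3) fixes the unit of allocation as the individual: "Adolescents will be randomized (1:1) to receive the behavioral intervention delivered via social media vs. standard of care". Section VI (Aim 2) describes what is demonstrated on the platform: "facilitated group discussions, message boards, and meet-ups via social media". It adds "Only one team will monitor and facilitate the sessions". Section VIII restricts the site to adolescents allocated to the intervention, with staff and clinicians. In one place it describes a single closed group entered by invitation; in another it refers to discussion groups in the plural.

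The only group size is in the recruitment paragraph of section VI (Aim 3): "We anticipate enrolling groups of 5 - 10 subjects based on preferences defined in Aim 1".

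Section VII (Aim 3) sets the decision rule: "We will consider a feasibility / acceptability estimate of 80% or higher among the 40 participants as evidence". The power statement takes 40 intervention participants, a true rate of 90% and a rate to exclude of 70%, "with 90% power (alpha=0.05, one-sided) using an exact test". The between-arm results have a planning role: "The secondary outcomes will assist in planning a larger randomized clinical trial through a future R01 grant". Aim 8 repeats the comparison for "retention in care and virological suppression 12 months after randomization", among other outcomes. No ICC, design effect, group term or standard-error method appears anywhere.

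**The concern.** Adolescents who share a chat share peers, discussion and timing, and peer support is both a mechanism of the intervention and a measured outcome. Acceptability, clinic connection and peer support could therefore be correlated within a chat, in one arm only. This is the partially nested design, in which a variance that treats everyone as independent is too small.

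Two things would be at stake. The 90% power assumes 40 independent responses and does not say so; with correlation, power falls and the real type I error rises. And since the between-arm results feed the planning of a larger trial, overstated precision could be carried forward.

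**Working it through.** **Inputs.** From section VII: n = 40 in the intervention arm, p0 = 0.70, p1 = 0.90, one-sided alpha 0.05, exact test. From section II (Aim 3): 40 per arm. From section VI: groups of 5 to 10, read for now as chat groups, so 40/10 = 4 to 40/5 = 8 groups. Assumed, because the documents give none: ICC 0.01, 0.05 and 0.10.

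**1. The plan's own figure.** Under independence the smallest r with P(X ≥ r | 40, 0.70) ≤ 0.05 is 34, since r = 33 gives 0.0553. At r = 34, alpha is 0.0238 and power is P(X ≥ 34 | 40, 0.90) = 0.9005. The stated 90% is right.

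**2. The same cut-offs with correlated groups.** The total is a sum of independent beta-binomial group counts with a = p(1 − ICC)/ICC and b = (1 − p)(1 − ICC)/ICC. The 80% rule corresponds to 32/40.

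| Group size | ICC | Alpha at 34/40 | Power at 34/40 | Pass 32/40, true 90% | Pass 32/40, true 70% |
|---|---|---|---|---|---|
| independent | 0 | 0.024 | 0.901 | 0.985 | 0.111 |
| 5 | 0.01 | 0.026 | 0.896 | 0.983 | 0.116 |
| 5 | 0.05 | 0.035 | 0.881 | 0.974 | 0.134 |
| 5 | 0.10 | 0.047 | 0.865 | 0.964 | 0.154 |
| 10 | 0.01 | 0.029 | 0.891 | 0.980 | 0.122 |
| 10 | 0.05 | 0.050 | 0.861 | 0.961 | 0.159 |
| 10 | 0.10 | 0.078 | 0.835 | 0.940 | 0.196 |

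The exact test starts well below its nominal level, so alpha stays at about 0.05 or less up to ICC 0.05 at every group size considered.

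**3. The other reading of the group size.** If batches of 5 to 10 are enrolled and then split 1:1, about 2 to 5 per batch reach the intervention arm. At ICC 0.10, groups of 2, 4 and 5 give power 0.890, 0.872 and 0.865, and alpha 0.029, 0.041 and 0.047.

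**4. Between-arm standard error.** With design effect DE = 1 + (m − 1)·ICC in one arm only, and equal variances and sizes, a standard error that ignores groups is too small by 1 − 1/√((1 + DE)/2). For m = 10 and ICC 0.10: DE = 1.90 and 1 − 1/√1.45 = 17.0%. For m = 5 and ICC 0.05: DE = 1.20 and 1 − 1/√1.10 = 4.7%. Over groups of 5 to 10 the shortfall is 1% to 2% at ICC 0.01, 5% to 10% at 0.05 and 9% to 17% at 0.10.

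**5. What passes to the larger trial.** Sample size normally uses the individual-level SD or event rate. The expected sample variance in the clustered arm is σ²(n − DE)/(n − 1). For m = 10 and ICC 0.10: √((40 − 1.90)/39) = 0.988, so the SD is low by 1.2%. For m = 5 and ICC 0.05: √((40 − 1.20)/39) = 0.997, so it is low by 0.3%. The shortfall in step 4 concerns interval width, which is a different quantity.

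**6. What a formal adjustment would cost.** With 4 to 8 clusters a corrected acceptability interval has 3 to 7 degrees of freedom. At ICC 0 it is wider by the ratio t/1.96, which is 1.21 (8 groups) to 1.62 (4 groups). An observed ICC of 0.05 would have a 95% interval of −0.12 to 0.47 with 8 groups of 5, and −0.06 to 0.67 with 4 groups of 10.

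**The case for a change.** The strongest case for acting is that the remedy is cheap. Say how chats are formed, record each intervention participant's chat, and state that the power assumes independence: one variable and a few sentences. Chat membership is not among the data listed for Aim 3, section VIII keeps names out of online communication, and the list linking study IDs to medical records is later deleted, so membership might be hard to reconstruct. Under the least favourable assumptions the effect is not trivial: with groups of 10 and ICC 0.10, alpha at 34/40 is 0.078 and the chance of passing 32/40 at a true 70% rises from 0.111 to 0.196. A single facilitating team limits differences between facilitators but not correlation among peers.

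The omission stands, and so does the arithmetic. Noting independence beside the power figure and keeping a chat log would be good practice. But entry to the site is by invitation and the research team monitors it, so a team running several chats would ordinarily know who was in each. The file to be deleted links study IDs to medical record numbers; it is not a record of chat membership. The less favourable figures need both large chats and an ICC that nothing in the documents supports. If there is one closed group, as one sentence in section VIII reads, between-group variation cannot be estimated at all.

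The usual adjustment also treats controls as singletons. Section VIII says clinic-day adolescent support groups are current practice, and there are two sites, so controls may be correlated too.

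**Conclusion.** No change to the plan is needed. Section VII commits to counts, percentages, medians, estimated differences and a point-estimate threshold. It names no confidence interval or between-arm test and does not expect a significant difference. Clustering leaves those point estimates unbiased. The power figure is correct on the ordinary independence assumption, and for groups of 5 to 10 it falls to 0.861–0.881 at ICC 0.05 and 0.835–0.865 at ICC 0.10. The pilot's decision is only modestly affected: a truly 90% acceptable programme still passes with probability 0.94 or more, while the chance of passing at a true 70% rises from 0.11 to between 0.12 and 0.20. The concern about planning the next trial largely falls away, because the individual-level SD is low by at most about 1.2%, and an ICC from 4 to 8 groups is too imprecise to use for sizing.

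How chats are formed and who was in each is detail that a competent team would settle and report. Whether to add small-sample cluster intervals in a pilot of 40 per arm is a fair trade-off on which statisticians will differ. These conclusions rest on assumed ICCs of 0.01 to 0.10 and on groups of 10 or fewer; a much larger ICC would weaken them.
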